5.3 Handling of Dropouts and Missing Data

Every effort will be made to minimize the number of dropouts and to document reasons for dropping out.

For FMMS score, the following imputation rules will be followed for missing data:

- a) Impute missing individual items at post-baseline visits using the Last-Observation-Carried-forward (LOCF) method.
- b) Impute missing individual items at baseline in the following two ways (i. imputed with a score of 0; ii. imputed with the first observed post-baseline value).

If there are no missing individual items for FMMS score at baseline, then the FMMS results will be shown only once, rather than once for each case specified in b) above.

5.4 Interim Analysis

The primary efficacy endpoint is at 24 weeks. Therefore, an interim analysis is planned after all randomized subjects who have not dropped out of the study have completed their 24 weeks visit to facilitate strategic discussion with regulatory agencies for future plans of the program.

5.5 Multicenter Study

Approximately 52 subjects will be randomized into the study at approximately thirty (30) sites in North America (i.e., United States), Eastern Europe (i.e., Ukraine), and Asia Pacific (i.e., Japan). A maximum of 12 subjects will be enrolled at each Assessment site, and a maximum of 16 subjects will be enrolled or treated at each Surgery or Comprehensive site, respectively.

5.6 Multiple Comparisons / Multiplicity

Multiplicity considerations will not be taken into consideration in the analyses for this Phase 2 study.

5.7 Examination of Subgroups

Analyses of the primary and secondary efficacy endpoints will be performed on the following subgroups of interest:

- Age at Informed Consent (18-<50 years of age, 50-75 years of age)
- Gender
- GOS-E score at screening (3, 4, 5, or 6)
- Baseline FMMS score (0-50, 51-100)

The primary efficacy endpoint will also be analyzed by lot and by percentage cell viability (\leq sample median value vs. $>$ sample median value). These subgroup analyses will be done for only the SB623 doses.

Analyses may also be performed on other subgroups of interest.

6.0 ANALYSIS POPULATIONS

6.1 Modified Intent-to-Treat Population

The Intent-to-Treat (ITT) population will include all randomized patients. All efficacy analyses will be conducted on the modified ITT (mITT) population, which is defined as all randomized patients who complete the surgical procedure. In analyses based on the mITT population, subjects will be analyzed according to their randomized treatment assignment. Analyses based on the mITT population will be considered the primary analyses of efficacy.

6.2 Per Protocol Population

The Per Protocol (PP) population will include all randomized patients who have no major protocol violations. Major protocol violations will be identified based on blinded data after the study is completed, but before database lock and the unblinding of the treatment group assignments. All efficacy analyses will be repeated on this population. In analyses based on the PP population, subjects will be analyzed according to their randomized treatment assignment. Analyses based on the PP population will be considered secondary analyses of efficacy.

6.3 Safety Population

The Safety population will include all study patients who undergo surgery (implant or sham). All safety analyses will utilize this population. In analyses based on the safety population, subjects will be analyzed according to the actual treatment received.

6.4 As Treated Population

The As Treated population will include all randomized patients who undergo surgery (implant or sham). In the event that a patient in the ITT population does not receive the treatment to which he/she was randomized (i.e., either no treatment or the wrong treatment), all efficacy analyses will be repeated on this population. Otherwise, no analyses will be performed on this population, because the analyses will be the same as for the ITT population. Therefore, no table shells will be produced for this population. In analyses based on the As Treated population, subjects will be analyzed according to the actual treatment received.

7.0 SUBJECT DISPOSITION

The numbers and percentages (based upon the ITT Population) of patients in the ITT Population, in the mITT Population, in the PP Population, in the Safety Population, in the As Treated Population, who completed the study, and who discontinued from the study before completion will be presented. For subjects who discontinued from the study before completion, the primary reason for early termination will be summarized using frequencies and percentages. For screen failures, the reason for screen failure will be summarized using frequencies and percentages.

8.0 DEMOGRAPHIC AND BASELINE CHARACTERISTICS

Subject demographic and body size measurements collected at the screening visit will be summarized using descriptive statistics for continuous variables (age at informed consent, height, weight, and BMI) and frequencies and percentages for categorical variables (sex, race, and ethnicity).

Medical history will be summarized by MedDRA system organ class (SOC) and Preferred Term using frequencies and percentages.

The GOS-E score, the Upper Extremity Scale Motricity Index, and the Lower Extremity Scale Motricity Index at screening will be summarized using descriptive statistics. The GOS-E score will also be summarized using counts and percentages.

HLA typing and ApoE4 and BDNF Val66Met genotyping will be summarized using counts and percentages.

9.0 SURGICAL PROCEDURE

Surgical procedure characteristics will be summarized using descriptive statistics or frequencies and percentages, as appropriate.

10.0 EFFICACY ANALYSES

10.1 Primary Efficacy Endpoint

The primary analysis will be a comparison of the least-squares mean (LSM) change from baseline in the Fugl-Meyer Motor Scale score of SB623 treated subjects (pooling all SB623 doses) to sham surgery control subjects at Week 24. A mixed model repeated measures (MMRM) analysis will be performed with terms for treatment (SB623 or sham surgery), visit, the treatment-by-visit interaction, the baseline Fugl-Meyer Motor Scale score, the baseline Fugl-Meyer Motor Scale score-by-visit interaction, the GOS-E score at screening, and the GOS-E score at screening-by-visit interaction. The Restricted Maximum Likelihood Estimation (REML) procedure will be employed using an unstructured covariance matrix. The LSM and standard error will be presented for the two treatments, together with a 95% confidence interval for the LSM. The difference in LSMs between treatments and corresponding 95% confidence interval will also be presented, together with the p-value from a two-sided, two-sample t-test based on the MMRM analysis, testing the null hypothesis that the LSMs for the two treatments are equal.

In addition, the primary efficacy endpoint, the change from baseline in the FMMS score at Week 24, will be analyzed to examine dose response. As for the primary analysis, a mixed model repeated measures (MMRM) analysis will be performed. The model will include terms for visit, the interaction between SB623 dose and an indicator variable for the Week 4 visit, the interaction between SB623 dose and an indicator variable for the Week 12 visit, the interaction between SB623 dose and an indicator variable for the Week 24 visit, the baseline Fugl-Meyer Motor Scale score, the baseline Fugl-Meyer Motor Scale score-by-visit interaction, the GOS-E score at screening, and the GOS-E score at screening-by-visit interaction. The Restricted Maximum Likelihood Estimation (REML) procedure will be employed using an unstructured covariance matrix. Dose will be treated as a continuous variable, and the control treatment will not be included in this analysis. The p-value from the test of the null hypothesis that the coefficient for the interaction between SB623 dose and the indicator variable for the Week 24 visit equals zero will be presented.

The primary efficacy endpoint will also be analyzed using an analysis of covariance model with the following terms: treatment, the presence of prior (i.e., at baseline) antibodies to donor cell HLA antigens, the interaction between treatment and the presence of prior antibodies to donor cell HLA antigens, the baseline FMMS score, and the GOS-E score at screening to test the null hypothesis that the coefficient of the interaction term equals 0.

The relationship between anti-HLA antibodies and the primary efficacy endpoint will be examined. Descriptive statistics for the primary efficacy endpoint will be presented by treatment group and whether or not the subject experienced an increase of antibodies to donor HLA antigens from baseline to Week 24. A normal approximation test will be used to test the null hypothesis that the differences in means between the pooled SB623 group and the control group are equal for subjects with an increase of antibodies to donor HLA antigens from baseline to Week 24 and those without an increase. Analogous analyses will be performed for whether or not a subject experienced the formation of antibodies post treatment to Week 24 (for subjects with no antibodies at baseline).

The primary efficacy endpoint will be summarized using descriptive statistics for the following subgroups of interest:

- Age at Informed Consent (18-<50 years of age, 50-75 years of age)
- Gender
- GOS-E score at screening (3, 4, 5, or 6)
- Baseline FMMS score (0-50, 51-100)
- Lot (SB623 doses only)
- Percentage cell viability (\leq sample median value, $>$ sample median value)

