3.4 Determination of Sample Size

For a two-sample t-test to show superiority of SB623 over sham surgery control, assuming 80% power, alpha of 0.05, a two-tailed test, and 3:1 randomization, a sample size of 48 (36 subjects in the treatment group and 12 subjects in the control group) is required. This assumes that the mean change from baseline to Week 24 in the FM-Motor Scale score is 10.0 for the treatment group (pooling all SB623 doses) and 3.0 for the control group, with an assumed standard deviation of 7.25 in each group. Based on an 8% upward adjustment to compensate for dropout patients, a total of approximately 52 subjects will be required. Since the analysis of efficacy is to be based on the modified ITT population, subjects will continue to be enrolled in the study until there are a total of approximately 52 subjects in the mITT population. The vast majority of subjects will be from outside of Japan; however, a sufficient number of Japanese patients are to be enrolled in order to address Japanese regulatory requirements.

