5.0 STATISTICAL CONSIDERATIONS

5.1 General Methodology

The statistical analysis of the data obtained from this study will be performed using SAS[®] version 9.4 or higher. All statistical tests will be performed at the 0.05 significance level.

The data collected in this study will be documented using summary tables and subject data listings. Continuous variables will be summarized using descriptive statistics, specifically the number of observations, mean, median, standard deviation, minimum and maximum. Categorical variables will be summarized by frequencies and percentages. For the most part results will be presented for the four treatment groups separately and the three SB623 dose groups pooled. The three SB623 dose groups will be pooled for all statistical tests comparing SB623 to sham surgery, except where noted otherwise (i.e., dose response analyses).

Data listings will be sorted by center and subject ID. All date fields will be presented in a format of ddmmmyyyy (i.e., 01Jan2018) in the listings.

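### The antibody-by-treatment comparison of the primary endpoint uses a normal reference although 12-13 sham patients are split in two, so it does not hold its 0.05 level

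*SAP*

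**What the plan says.** Three paragraphs of SAP Appendix A, Section 10.1, matter here.

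- The primary analysis is an MMRM comparison of pooled SB623 with sham at Week 24, tested against a t distribution.
- For antibodies present before treatment, the SAP fits an ANCOVA with treatment, prior antibodies, their interaction, baseline FMMS and GOS-E, and tests the interaction coefficient.
- For antibodies that rise after treatment, it changes method. Patients are grouped by arm and by "whether or not the subject experienced an increase of antibodies to donor HLA antigens from baseline to Week 24". The treatment differences in the two groups are then compared: "A normal approximation test will be used to test the null hypothesis that the differences in means" are the same. The SAP adds: "Analogous analyses will be performed for whether or not a subject experienced the formation of antibodies post treatment to Week 24". This second analysis is limited to patients with no antibodies at baseline.

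Section 5.1 applies to both: "All statistical tests will be performed at the 0.05 significance level". No passage states the variance estimator, the sidedness, the expected share of patients with a rise, a minimum cell size or a small-sample correction for these two tests.

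**The concern.** The contrast is built from four cell means: SB623 and sham, each with and without a rise. Its variance is dominated by the smallest cell, and sham is the small arm at 3:1 allocation. Sham surgery does not penetrate the dura (Protocol Section 6.0), so those patients receive no donor cells, and a rise in antibodies to donor HLA may be uncommon among them. A normal reference treats the estimated variance as if it were known. When most of that variance comes from two or three patients, the true reference distribution has much heavier tails, and the test rejects too often.

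At stake is a false statement that antibodies alter the effect of SB623. The result goes into the final report as Table 14.2.4.10. Table 14.2.24.2 reports a closely related interaction from an ANCOVA, so readers would see two similar p-values drawn from different reference distributions. Neither is adjusted for multiplicity (Section 5.6).

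**Working it through.** **1. Arm sizes.** The inputs are in SAP Section 3.4: "assuming 80% power, alpha of 0.05, a two-tailed test, and 3:1 randomization, a sample size of 48", split as "36 subjects in the treatment group and 12 subjects in the control group". The assumed mean change "is 10.0 for the treatment group (pooling all SB623 doses) and 3.0 for the control group". For the spread of the changes, the same section plans "with an assumed standard deviation of 7.25 in each group".

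Sham n = (1 + 1/3) × (1.960 + 0.842)² × (7.25/7.0)² = 1.333 × 7.849 × 1.0727 = 11.2, rounded up to 12. SB623 n = 3 × 12 = 36, total 48. Noncentral-t power at 36 and 12 is 80.9%, so the plan's figure reproduces. With 8% added, 48 × 1.08 = 51.8, about 52, or 39 and 13 at 3:1. The sham arm is therefore 12-13 patients.

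**2. The statistic.** With d = (SB623 minus sham, rise) − (SB623 minus sham, no rise), two variance estimators are natural:

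- unpooled: Σ sᵢ²/nᵢ over the four cells;
- overall pooled: s² × Σ 1/nᵢ, with s² on N − 4 degrees of freedom.

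The ratio is referred to ±1.96 (two-sided, assumed).

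**3. Why the sham cell dominates.** Take 10 SB623 with a rise, 29 without, 2 sham with, 11 without. Then Σ 1/nᵢ = 0.100 + 0.034 + 0.500 + 0.091 = 0.725, and the two-patient cell supplies 0.500/0.725 = 69% of it. The Satterthwaite df of the unpooled variance is 0.725² / (0.100²/9 + 0.034²/28 + 0.500²/1 + 0.091²/10) = about 2.1.

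**4. Simulated type I error** (200,000 data sets per layout, normal data, equal SD, nominal 5%). Cells are SB623 with rise / SB623 without / sham with / sham without.

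| Cells | Unpooled, 1.96 | Overall pooled, 1.96 | Unpooled, Satterthwaite t | Pooled t, N − 4 df |
|---|---|---|---|---|
| 10/29/2/11 | 13.3% | 5.7% | 8.8% | 5.1% |
| 20/19/2/11 | 13.8% | 5.6% | 9.1% | 5.0% |
| 10/29/3/10 | 8.9% | 5.5% | 5.9% | 4.9% |
| 20/19/4/9 | 7.5% | 5.6% | 5.4% | 5.0% |
| 20/19/6/7 | 6.5% | 5.6% | 4.9% | 5.0% |

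Over all layouts run at N = 48 to 52, the unpooled version gives:

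- 11.7-14.0% with a smaller sham cell of 2;
- 8.6-9.2% with 3;
- 7.2-7.8% with 4;
- 6.4-7.5% with 5-6.

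The overall pooled version has an exact value that does not depend on cell sizes: 2 × P(t₄₄ > 1.96) = 5.63% at N = 48 and 2 × P(t₄₈ > 1.96) = 5.58% at N = 52. Pooling across arms within each antibody group lies between the two, mostly 5.6-7.1%. It reaches 7.6-9.7% with only 4 SB623 patients in the small group, and about 14% with 2 and 2.

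**5. Formation subset.** The number of baseline-negative patients is not given; 36 and 24 are assumed. Pooled: 5.9% and 6.4%. Unpooled: 10.5-11.9% with a sham cell of 2, 8.0-8.6% with 3, and 7.3% in the one layout run with 4.

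**6. How likely is a small sham cell?** The rate of a rise among sham patients is not in the documents, so it is assumed. The smaller of the two sham cells, from Binomial(12, p) to Binomial(13, p):

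| Assumed rate | 0-1 patients | 2-4 patients | 5 or more |
|---|---|---|---|
| 5% | 88-86% | 12-14% | under 0.1% |
| 10% | 66-62% | 34-37% | under 1% |
| 20% | 27-23% | 65-67% | 7-10% |
| 30% | 9-6% | 65-59% | 27-34% |
| 50% | under 1% | 38-26% | 61-73% |

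With 0 patients the contrast cannot be estimated. With 1 the unpooled variance has no estimate for that cell.

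**The case against.** The strongest reply is that the size of the problem rests on two things the documents do not say. One is the variance estimator: an overall pooled standard error matches the equal-SD planning assumption in Section 3.4, and the error is then 5.6%, a trivial excess. The other is the antibody rate: at about 50%, both sham cells hold 5 or more with probability 61-73%, while at low rates the likely outcome is a cell of 0-1, to which the 7-14% does not apply. Protocol Section 4.2 reports no antibody responses in the earlier stroke study, which makes high rates hard to presume. Both points stand, so the size must be given as a conditional range. They do not make the test valid: it exceeds 5% under either estimator, and the unstated choice moves the error between 5.6% and 14%.

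It can also be said that SAP Appendix D, Section 7.0, already plans an ANCOVA interaction F-test for post-treatment antibodies. Its grouping is a significant increase at any post-baseline visit, whereas Section 10.1 uses any rise from baseline to Week 24. It is a related analysis and does not replace this one. Section 5.6 of Appendix D also acknowledges that groups formed after baseline are not true subgroups, a limit that no choice of reference distribution removes.

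A reader might infer more than the documents support:

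- That the error simply is 7-14%. This needs an unpooled standard error and a smaller sham cell of 2-4.
- That false claims become two to three times as likely. Only a sham cell of 2 gives this (11.7/5 = 2.3 to 14.0/5 = 2.8); cells of 3-4 give about 1.4-1.8 times (7.2/5 to 9.2/5).
- That confidence limits are too narrow. None are planned for this test.

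**Conclusion.** The test as written does not hold the 0.05 level. The excess is small (about 5.6%, or about 6% in the formation subset) if the variance is pooled over all four cells. It is material (about 7-14%) if the variance is unpooled and the smaller sham cell has 2-4 patients, and about 6.4-7.5% at 5-6. If sham rises are rare, the test may not be computable at all, and the SAP has no rule for that. These figures assume normal data, equal variances and a two-sided test.

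The consequence is confined to a supportive analysis on a post-baseline grouping. The primary MMRM comparison does not use this test and is unaffected. The point is still worth correcting, because the SAP already uses a suitable form of test in the paragraph before it.

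**What to change.** In Section 10.1, replace the normal-approximation test with the treatment-by-antibody-rise interaction from an ANCOVA of Week 24 FMMS change, with baseline FMMS and GOS-E as covariates and a t or F reference on residual degrees of freedom (four cells and two covariates leave 48 − 6 = 42 to 52 − 6 = 46). This is the prior-antibody model of the same section with the antibody factor changed; the Appendix D test has the same form without GOS-E. Use it for the formation analysis too. When a sham cell holds 0 or 1 patients, report descriptive statistics only. Keeping the unpooled variance with Satterthwaite df is not enough: the error is still 6.2-9.1% with a sham cell of 2.

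The change needs SAP wording and reprogramming of one table, and no new data. P-values may move in either direction, because covariate adjustment and pooling alter both the estimate and its standard error. The SAP addendum (Section 3.0) records that interim results have been unblinded, so the change should be reported as a deviation in the study report (Protocol Section 18.8), with both results shown if the planned test has already been run.

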10.2 Secondary Efficacy Endpoints

The change from baseline in the Disability Rating Scale (DRS) score at Week 24 among all patients, the change from baseline in the Action Research Arm Test (ARAT) total score at Week 24 among upper extremity deficit patients, the change from baseline in Gait Velocity at Week 24 among lower extremity deficit patients, and the change from baseline in the two NeuroQOL subdomain T scores (Upper Extremity Function (Fine Motor ADL) and Lower Extremity Function (Mobility)) at Week 24 among upper and lower extremity deficit patients, respectively, will each be analyzed in a manner analogous to that for the primary efficacy endpoint.

In addition, each of these secondary efficacy endpoints will be analyzed to examine dose response. Analogous statistical methodologies to those used for evaluating dose response for the primary efficacy endpoint will be used for these endpoints.

The proportions of SB623 treated subjects (pooling all SB623 doses) scoring either 7 (much better) or 6 (a little better, meaningful) on the Global Rating of Perceived Change (from Baseline) - Subject at Week 24 and on the Global Rating of Perceived Change (from Baseline) - Clinician at Week 24 will be compared to the corresponding proportions of sham surgery control subjects using a logistic regression model with a term for treatment (SB623 or sham surgery) and the baseline Fugl-Meyer Motor Scale score and the GOS-E score at screening as continuous covariates. The endpoints for these analyses are dichotomized variables based on the Global Rating of Perceived Change score (≥ 6 vs. < 6). In addition, both of these secondary efficacy endpoints will be analyzed to examine dose response using a logistic regression model with SB623 dose, the baseline Fugl-Meyer Motor Scale score, and the GOS-E score at screening as continuous covariates in the model. The control treatment will not be included in this analysis.

The secondary efficacy endpoints will be summarized using descriptive statistics or frequencies and percentages for all of the same subgroups of interest as for the primary efficacy endpoint except lot and percentage cell viability.

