The fourth, fifth, sixth, seventh, and eighth exploratory efficacy endpoints will be summarized using frequencies and percentages and will be analyzed using a logistic regression model with a term for treatment (SB623 or sham surgery) and the baseline value of the endpoint and the GOS-E score at screening as continuous covariates.

The analyses of the last five exploratory efficacy endpoints will be addressed in separate documents.

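### The SAP names no estimator, test or zero-cell method for its responder endpoints, although zero responders among about 13 sham patients is a realistic outcome

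*SAP*

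**What the plan says.** SAP Appendix A (main study), 10.2, dichotomises the subject and clinician global ratings at a score of 6 or more. The SB623 proportions "will be compared to the corresponding proportions of sham surgery control subjects using a logistic regression model with a term for treatment", with baseline FMMS and screening GOS-E as continuous covariates. Section 10.3 says that exploratory endpoints 4 to 8 "will be analyzed using a logistic regression model with a term for treatment (SB623 or sham surgery") and two covariates, the baseline value and GOS-E. These endpoints are gains in UE-FM, LE-FM, total FMMS and ARAT, and a gain of one gait-speed level. Section 5.2 repeats both models, and protocol 18.2.2.2 (item E) gives the same model for the global ratings.

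None of these sections names an estimation method, a type of test, an interval method, or a rule for an empty cell or non-convergence. Elsewhere the SAP is specific: 10.1 names REML, the covariance structure and the test for the primary analysis, and 12.1 names Fisher's exact test for adverse events.

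The sample size (SAP 3.4) rests on this statement: "a sample size of 48 (36 subjects in the treatment group and 12 subjects in the control group) is required". It then adds: "Based on an 8% upward adjustment to compensate for dropout patients, a total of approximately 52 subjects will be required".

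**The concern.** A 3:1 allocation puts about 13 of 52 patients on sham. Endpoints 4, 5, 7 and 8 are restricted to patients with an upper or lower limb deficit, so their sham groups can be smaller. If no sham patient responds, the sample odds ratio has zero in its denominator. The maximum-likelihood treatment coefficient then diverges, its standard error diverges faster, and the Wald p-value goes towards 1. This happens in the data pattern most favourable to SB623. With no fallback written down, any rescue would be chosen after the pattern had been seen.

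At stake is the usability of the odds ratio, interval and p-value for two secondary and five exploratory endpoints.

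**Working it through.** **1. The plan's own figure.** Inputs from SAP 3.4: "assuming 80% power, alpha of 0.05, a two-tailed test, and 3:1 randomization"; the mean change "is 10.0 for the treatment group (pooling all SB623 doses) and 3.0 for the control group"; and an SD of 7.25 in both arms. With 36 and 12 patients the noncentrality is 7 / (7.25 × √(1/36 + 1/12)) = 2.90, and two-sided t-test power is 80.9%. With 33 and 11 it is 77.3%. So 48 reproduces. For dropout, 48 × 1.08 = 51.8 and 48 / 0.92 = 52.2, both about 52, or 39:13 at 3:1.

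**2. Responder rates implied for endpoint 6 (FMMS gain ≥ 10), assuming normal changes.**
- Sham: 1 − Φ((10 − 3)/7.25) = 1 − Φ(0.966) = 16.7%.
- SB623: 1 − Φ((10 − 10)/7.25) = 50%.

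**3. Chance of no sham responder, (1 − p)^n.** At p = 16.7%: 9.3% with n = 13, 11% with n = 12, and 23% with n = 8 (a subset size and rate assumed for illustration). Other sham rates with n = 13, all assumed:

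| Sham rate | P(0 of 13) |
|---|---|
| 10% | 25% |
| 15% | 12% |
| 20% | 5.5% |
| 25% | 2.4% |
| 30% | 1.0% |
| 40% | 0.1% |

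**4. Power, two-sided 0.05.** The unadjusted figures come from exact enumeration of every 2×2 table, with Wald counted as non-significant when a cell is empty. The adjusted figures come from 2,500 simulated trials with two null covariates (Monte Carlo standard error at most √(0.25/2500) = 1 point).

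| SB623:sham | Rates, sham / SB623 | Wald | Firth | Fisher | Adjusted Wald / Firth |
|---|---|---|---|---|---|
| 39:13 | 16.7% / 50% (implied, endpoint 6) | 44.6% | 56.6% | 49.2% | 44.5% / 56.8% |
| 39:13 | 10% / 40% (assumed) | 18.5% | 52.7% | 50.2% | 19.9% / 52.7% |
| 39:13 | 20% / 50% (assumed) | 38.9% | 46.4% | 38.7% | not run |
| 39:13 | 30% / 60% (assumed) | 44.8% | 45.8% | 37.0% | 43.1% / 44.2% |
| 24:8 | 16.7% / 50% (size and rates assumed) | 10.9% | 39.0% | 30.5% | 11.6% / 34.2% |

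Unadjusted losses at 39:13, Firth minus Wald, are 12.0, 34.2, 7.5 and 1.0 points, in row order. In simulated trials with zero sham responders the Wald test never rejected. In the 39:13 scenarios with a true effect, Firth rejected in 96% to 100% of such trials.

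**5. Type I error at 39:13, equal rates of 10% to 30%.** Firth: 3.1% to 4.6%. Plain likelihood-ratio test: 5.2% to 7.4%.

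**The case against.** The strongest reply is that neither maximum likelihood nor the Wald test appears in the documents. They are the usual reading of an unqualified logistic regression, and a likelihood-ratio test would not lose power in this way. That stands as a matter of attribution: a reader might infer that the SAP prescribes the Wald test, and it does not. It does not close the gap, because the likelihood-ratio test runs above 5% here and the odds ratio and its upper limit stay unbounded.

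Second, the 16.7% sham rate belongs to exploratory endpoint 6 alone. No document gives a sham rate for the global ratings, where a response includes a small but meaningful improvement reported after blinded sham surgery, so a much higher rate is plausible. At 30% or more, zero of 13 has a chance of 1% or less. Nor do the documents give rates or sizes for the limb subsets, whose scales and cut-offs differ from total FMMS. This stands, and it rules out the tempting inference that all seven analyses lose much of their power.

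Third, analyses that separation cannot disturb are already planned: MMRM of the underlying continuous scores, cumulative distribution plots with a Kolmogorov-Smirnov test, t-tests by visit on the global ratings (SAP 10.4), and responder counts for the exploratory endpoints, which would show 0 of 13 plainly. These soften the consequence but do not supply a valid adjusted responder test.

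Fourth, Firth is not the only remedy. Fisher's exact test comes close at 10% versus 40%, but falls behind at the other rates shown and drops the planned covariates.

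**Conclusion.** The point holds as a gap in specification with a measurable cost. For exploratory endpoint 6, on the plan's own means and SD and assuming normality, there is a 9% chance of an inestimable odds ratio with 13 sham patients, and about 12 points of power are lost if Wald tests are used (45% against 57%). For the global ratings and the limb-subset endpoints the size is unknown: at 39:13 it is about 34 points at 10% versus 40% and about 1 point at 30% versus 60%, and a smaller sham group raises the risk of an empty cell.

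A reader might go on to infer that the trial's main conclusion is at risk. The documents do not support that: the primary endpoint is a continuous change analysed by MMRM, and the plan claims no power for any responder endpoint. The change should be made, but it concerns secondary and exploratory results only.

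**What to change.** In SAP 5.2, 10.2 and 10.3, state that all binary efficacy endpoints are analysed by Firth penalised-likelihood logistic regression with the covariates already listed, reporting profile penalised-likelihood 95% confidence intervals and penalised likelihood-ratio p-values. Carry the same wording into section 7.2 of the supplement for the Japanese submission, which repeats the global-rating model.

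If the responder results are already unblinded, add this as a labelled sensitivity analysis instead of replacing the planned model. That condition matters because the addendum to the main SAP (section 3.0) records that post-hoc analyses were added after the interim results were unblinded.

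The cost is about one sentence in each section and one option in the SAS procedure. The downside is slight shrinkage of the odds ratio towards 1.
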